### 5.3 Analysis of Exploratory Endpoints

Exploratory efficacy analyses will include estimation of the proportion of patients achieving each of the following endpoints:

- For patients who have positive PET scans at EOI: CR at 12 months, as determined by the IRC and by the investigator on the basis of PET-CT scans
- CR at 12 months, as determined by the investigator on the basis of CT scans alone (BO29561)
- CR at 12, 24, and 30 months in patients with previously untreated FL, as determined by the investigator using modified Cheson 2007 criteria (BO29563)
- Additional descriptive analysis based on TP53 status will be performed on the following endpoint: CR at EOI, as determined by the IRC on the basis of PET-CT scans (BH29812)

Point estimates will be presented, along with the corresponding two-sided 90% Clopper-Pearson exact CIs. Patients without a post-baseline tumor assessment will be considered non-CRs and non-responders, respectively.

Exploratory efficacy analyses will also be performed on the following endpoints:

- PFS, defined as the time from initiation of study treatment to first occurrence of disease progression or relapse, as determined by investigator on the basis of CT scans alone, or death from any cause
- EFS, defined as the time from initiation of study treatment to any treatment failure, including disease progression or relapse, as determined by investigator on the basis of CT scans alone, initiation of new anti-lymphoma therapy, or death from any cause, whichever occurs first
- DFS, defined, among patients achieving a CR, as the time from the first occurrence of a documented CR to relapse, as determined by the investigator on the basis of CT scans alone, or death from any cause, whichever occurs first
- DOR, defined as the time from the initial response to disease progression or death among patients who have experienced a CR or PR during study (Study BO29561/BO29562).
- OS, defined as the time from initiation of study treatment to death from any cause


Brookmeyer and Crowley ([1982](#)). In addition, landmark estimates of the proportion of patients who are event free at 6 months, 9 months, 1 year, and 2 years will be provided, along with 95% asymptotic CIs using Greenwood's formula for standard errors.

## **5.4 Interim Analyses**

It is anticipated that at least one interim analysis will be conducted during the expansion phase of the study, when at least 15 patients in one treatment arm have been evaluated for PET-CT–defined CR at the EOI.

## **6 Safety Analyses**

Safety analyses will be based on all patients who received at least 1 component of study medication. For safety analyses, patients will be reported by the treatment actually received. Patients who only received certain treatments from a combination group, but not all, will be reported by the planned treatment group.

Study data will be summarized separately for each phase. Data from the dose-escalation/safety run-in phase will be summarized by cohort (assigned dose level). Data from the expansion phase will be summarized by histological subtype (i.e., FL or DLBCL) and treatment group if applicable.

### **6.1 Exposure**

Exposure summaries will be done by study period, i.e. there will be separate outputs for induction and post-induction phase. Exposure summaries will also be done by cycle if necessary.

#### **6.1.1 Extent of Exposure to Study Drug**

At least one component of study treatment (i.e. obinutuzumab, rituximab, atezolizumab, polatuzumab vedotin, venetoclax, lenalidomide, idasanutlin or chemotherapy as defined in section 2.2) per cycle requires a received dose of >0 to be considered as a received cycle.

#### **6.1.2 Dose Intensity**

The dose intensity will be calculated based on the total received dose as compared to total planned dose (based on planned dose of first intake). Patients who withdrew prematurely from one study drug component but are still receiving other components of the study drug will be included in the calculation of the dose intensity up until the last day on which they received any study drug component.

E.g a patient in Atezo-G-Benda arm in BO29563 in induction had 5 doses of G with last dose on Cycle 3 Day 1, and 7 doses of Bendamustine with last dose on Cycle 4 Day 1. Number of expected doses for G would be 6, dose intensity for G would be  $5 * 1000 \text{ mg} / 6 * 1000 \text{ mg}$ .

The intensity categories are: <60%, 60 - <80%, 80 - <90%, >=90%, Missing. Summary statistics (mean, s.d., median, range) will also be used to summarize the dose intensity.

Dose intensity will be summarized separately for the induction and post-induction phase. For drugs in Prednisone category in BO29563, i.e. Methylprednisolone, Prednisone, Prednisolone and Dexamethasone, dose intensity is calculated for the whole category as number of actually received doses divided by number of expected doses up to the last time point any component of study drug was received.

## **6.2 Adverse Events**

### **6.2.1 General AE Reporting**

Listings will include all AEs. A flag will indicate to which study period an AE is assigned to: before treatment, initial/induction treatment, maintenance/consolidation treatment or follow up.

Study periods are as defined in Section [2.3.4](#). An AE is assigned to a period using the AE onset date, Unless otherwise specified, AE and SAE summary tables will be restricted to those that are treatment emergent, defined as starting on or after the day of first dose of any drug. For summary tables on the follow-up period, no upper time window is implemented, that is, all AEs from start of follow-up onwards will be included.

Generally AE will be summarized by study period.

In addition selected adverse events and AESI (see categories in subsequent tables) may be summarized by treatment cycle. An AE will be assigned to a cycle based on the AE onset day relative to cycle start day. Cycle start day is the first day on which any study medication was administered. AEs with onset on cycle start day will be included in the respective cycle.

In studies BO29561, BO29562 and BO29563 AESI based on tickbox in CRF page and on causality to any study drug will be reported separately .

### **6.2.2 Selected AEs and AE of Special Interest (AESI)**

Selected AE and AESI were defined based on the clinical experience with study treatment components that represent an IMP. Also anticipated potentially overlapping toxicities as specified in respective study protocols need to be taken into account.

Definitions for selected AE and AESI are provided in subsequent tables.

Selected AE Category	Definition	BO29563	BO29562	BO29561	BH29812	BH39147	GO29833	GO29834
Thrombocytopenia	SMQ "HAEMATOPOIETIC THROMBOCYTOPENIA narrow" (20000031n)	x	x	x	x	x	x	x
Hepatitis B reactivation/newly occurring	PT 'HEPATITIS B'	x	x	x	x	x	x	x
Cardiac AE	SOC "CARDIAC DISORDERS"	x	x	x	x	x	x	x
Infusion Related Reaction (IRR)	PT 'INFUSION RELATED REACTION' and related to at least one component of study treatment and event occurred within 24 hours or during infusion and tickbox 'Systemic Infusion Reaction' ticked (This definition was applied in BO29563- study lead BioStats/SPA please check if this is valid for your study)	x	x	x	x	x	x	x
Infections	SOC 'INFECTIONS AND INFESTATIONS'	x	x	x	x	x	x	x
Neutropenia	Roche Standard AEGT "NEUTROPENIA AND ASSOCIATED COMPLICATIONS" (for BO29561-3: including late onset and prolonged neutropenia) (SMQ Haematopoietic leukopenia narrow for GO29833/834)	x	x	x	x	x	x	x

Selected AE Category	Definition	BO29563	BO29562	BO29561	BH29812	BH39147	GO29833	GO29834
Prolonged neutropenia	Initial ANC < 1.0 × 10  /L that is still present 28 days after treatment with GA101				x	x		
Late onset Neutropenia	ANC < 1.0 × 10  /L occurring ≥ 28 days after ga101 infusion has been completed/stopped				x	x		
Gastrointestinal perforation	SMQ "GASTROINTESTINAL PERFORATION" (20000107 narrow).	x	x	x	x	x	x	x
Peripheral Neuropathy (motor/and or sensory)	SMQ Peripheral neuropathy wide			x			x	x
Dose Limiting Toxicity	CRF tickbox				x			
Drug-drug interactions	Single PT		x					

AE of Special Interest	Definition	BO29563	BO29562	BO29561	BH29812	BH39147	GO29833	GO29834
Drug induced liver injury	<del>Respective tickbox for AESI on CRF page ticked</del>				x	x	x	x
Suspected transmission of infectious agent	<del>Respective tickbox for AESI on CRF page ticked</del>				x	x	x	x
Grade 4 thrombocytopenia	SMQ "HAEMATOPOIETIC THROMBOCYTOPENIA narrow" (20000031n)						x	
Grade ≥ 3 infection	SOC						x	
Grade ≥ 3 thrombocytopenia or Grade 2 thrombocytopenia if associated with hemorrhage/bleeding	?				x	x		
Grade ≥ 2 diarrhea	?				x	x		
Grade ≥ 3 neutropenia, including febrile neutropenia	SMQ HAEMATOPOIETIC LEUKOPENIA (narrow)				x	x		
Grade ≥ 2 C. difficile infection	?				x	x		
Immune-related Pneumonitis	SMQ INTERSTITIAL LUNG DISEASE (narrow)	x	x	x				
Immune-related Colitis	HLT COLITIS (excluding infective)	x	x	x				
Immune-related Adrenal insufficiency	AEGT Atezolizumab comprehensive adrenal insufficiency search - 22 Jul 2015	x	x	x				
Immune-related Diabetes Mellitus	AEGT Atezolizumab Diabetes/DKA (excludes Hyperglycemia)	x	x	x				

AE of Special Interest	Definition	BO29563	BO29562	BO29561	BH29812	BH39147	GO29833	GO29834
Immune-related Pancreatitis	ATEZOLIZUMAB PANCREATITIS AEGT	x	x	x				
Immune-related hypothyroidism	Hypothyroidism SMQ (wide)	x	x	x				
Immune-related hyperthyroidism	Hyperthyroidism SMQ (narrow)	x	x	x				
Immune-related Hepatitis	HEPATIC FAILURE, FIBROSIS AND CIRRHOSIS AND OTHER LIVER DAMAGE-RELATED CONDITIONS SMQ (narrow); HEPATITIS NON-INFECTIOUS SMQ (narrow); LIVER RELATED INVESTIGATIONS, SIGNS AND SYMPTOMS SMQ (narrow)	x	x	x				
Immune-related Guillain-Barré syndrome	GUILLAIN-BARRE SMQ (narrow)	x	x	x				
Immune-related Myasthenia gravis	HLT MYASTHENIA GRAVIS AND RELATED CONDITIONS	x	x	x				
Immune-Related Nephritis	HLT glomerulonephritis and nephrotic syndrome or HLT nephritis NEC	x	x	x				
Immune-related Meningitis	Noninfectious meningitis SMQ (narrow)	x	x	x				
Immune related Encephalitis	Noninfectious encephalitis SMQ (narrow)	x	x	x				
Immune-related myositis	HLT muscle infections and inflammations; HLT muscular autoimmune disorders	x	x	x				

AE of Special Interest	Definition	BO29563	BO29562	BO29561	BH29812	BH39147	GO29833	GO29834
Immune-related Rhabdomyolysis	SMQ Rhabdomyolysis / myopathy (narrow)	x	x	x				
Immune-related Rash	AEGT EGFR Associated Skin Reactions	x	x	x				
<del>IRR/Hypersensitivity</del> Infusion Related Reactions	<del>AEGT Kadcyla specific AEGT-Infusion Related reactions/Hypersensitivity (type 1) 14 Feb 2013</del>  PTs 'Infusion Related Reaction', 'Cytokine Release Syndrome' Only AE with onset on same day or within 1 day of Atezo infusion are flagged	x	x	x				
Systemic immune Activation	Systemic Immune Activation (PT), Cytokine Release Syndrome (PT)	x	x	x				
Immune Related Ocular Inflammatory Toxicity	AEGT ATEZOLIZUMAB OCULAR INFLAMMATION TOXICITY)	X	X	X				
Immune-related Vasculitis	Vasculitis (SMQ) narrow	x	x	x				
Immune-related Hypophysitis	hypothalamic and pituitary disorders NEC (HLT)	x	x	x				
Immune-related Myocarditis	<del>Noninfectious myocarditis (HLT), Noninfectious pericarditis (HLT), Cardiac failure (SMQ) narrow</del> AEGT Atezolizumab Myocarditis Immune Related	x	x	x				

AE of Special Interest	Definition	BO29563	BO29562	BO29561	BH29812	BH39147	GO29833	GO29834
Immune-related Severe Cutaneous Reaction	Severe cutaneous adverse reactions (SMQ) narrow	x	x	x				
Secondary malignancy	"Malignant or Unspecified Tumours"(2000009w), starting 6 months after the first study drug intake or later	x	x	x	x	x	x	x
Tumor Lysis Syndrome	PT: 'TUMOUR LYSIS SYNDROME'	x	x	x	x	x	x	x
Auto-Immune Hemolytic Anaemia	Haemolytic Disorders (SMQ) narrow	x	x	x				

PT = Preferred Term , HLT = High Level Term , HLGT = High Level Group Term , SOC = System Organ class, SMQ=Standard MedDRA Queries

For Atezo specific AESI (i.e. all categories of AESI listed in table except secondary malignancy and TLS) only AE with causality to Atezo suspected and onset on or after start of cycle 2 are considered.

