## **1.2 BACKGROUND ON OBINUTUZUMAB**

Obinutuzumab (also known as GA101) is a novel glycoengineered type II anti-CD20 antibody. Compared with rituximab, obinutuzumab is characterized by more potent direct B-cell death induction and increased affinity for FcγRIII receptors expressed on natural killer (NK) cells, macrophages, and monocytes, resulting in enhanced antibody-dependent cellular cytotoxicity (ADCC) and antibody-dependent cellular phagocytosis (ADCP) (Beers et al. 2010; Mössner et al. 2010; Herter et al. 2014). Together, these characteristics confer obinutuzumab with enhanced immune effector functions and B cell–depleting activity compared with rituximab.

Obinutuzumab is approved for the treatment of patients with relapsed or refractory (R/R) FL and is approved for use in combination with chlorambucil for the treatment of patients with previously untreated chronic lymphocytic leukemia (CLL). Obinutuzumab is also approved for use in combination with bendamustine followed by obinutuzumab maintenance for the treatment of patients with FL who did not respond to or who progressed during or after treatment with rituximab or a rituximab-containing regimen. Obinutuzumab continues to be investigated in a large clinical program.

Background on rituximab can be found in Sections 1.1 and 1.5.

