## **3. STUDY DESIGN**

### **3.1 DESCRIPTION OF STUDY**

#### **3.1.1 Overview of Study**

This Phase Ib/II, open-label, multicenter, non-randomized, dose-escalation study will evaluate the safety, efficacy, and pharmacokinetics of obinutuzumab in combination with idasanutlin and venetoclax in patients with R/R FL and rituximab in combination with idasanutlin and venetoclax in patients with R/R DLBCL. The study will include an initial dose-escalation phase followed by an expansion phase. The dose-escalation phase is designed to determine the RP2Ds and regimen for idasanutlin and venetoclax in combination with obinutuzumab for FL patients and in combination with rituximab for DLBCL patients. Dose escalation starts with idasanutlin and venetoclax in combination with obinutuzumab in all patients (FL and DLBCL) until the MTD (Regimen A) *or until Sponsor decision based on clinical judgment* (see Section 3.1.2), followed by:

- Dose confirmation and potential dose escalation in patients with DLBCL for idasanutlin and venetoclax in combination with rituximab to determine the RP2Ds for this combination
- Dose confirmation and potential dose escalation in patients with FL with a different regimen (Regimen B, obinutuzumab given alone in Cycle 1 followed by idasanutlin, venetoclax, and obinutuzumab in combination in Cycles 2–6) to determine the RP2Ds for this regimen

The RP2Ds and regimen for FL and RP2Ds for DLBCL will be decided at the end of dose-escalation phase. Different RP2Ds and/or regimens may apply for FL and DLBCL, respectively.

[figure not shown]
In the expansion phase, patients with FL will receive idasanutlin and venetoclax at the RP2Ds of the selected regimen (Regimen A or B) in combination with obinutuzumab, and patients with DLBCL will receive idasanutlin and venetoclax at the RP2Ds in combination with rituximab (see Section 3.1.3).

Patients with R/R FL enrolled in the dose-escalation and expansion phases may be eligible to receive post-induction treatment (referred to as maintenance) with obinutuzumab, venetoclax, and idasanutlin (see Sections 3.1.2.2 and 3.1.3, respectively, for details on the treatment regimens).

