### **Combination of Rituximab, Idasanutlin, and Venetoclax in Patients with DLBCL in the Bridging Cohorts**

Following the identification of the MTDs for idasanutlin and venetoclax in combination with obinutuzumab, *or following Sponsor decision based on clinical judgment*, a bridging cohort of patients with DLBCL will be opened to *repeat the last dose tested* in combination with rituximab instead of obinutuzumab (375 mg/m^2 on Day 1 of each cycle; see [Figure 4](#) and [Table 1](#)).

If safety and tolerability allow, idasanutlin and venetoclax dose escalations may be explored in combination with rituximab in patients with DLBCL until identification of new MTDs (see [Figure 4](#)).

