### **5.1.2 Risks Associated with Rituximab**

The following adverse events are considered to be important risks associated or potentially associated with rituximab: IRRs, infections (including severe infections), PML, hepatitis B reactivation, neutropenia (including prolonged neutropenia), TLS, impaired immunization response, severe skin reactions (Stevens-Johnson syndrome/toxic epidermal necrolysis), and GI perforation. Details for these risks are provided below; refer to the Rituximab Investigator's Brochure for full information.

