### **5.2.4 Selected Adverse Events**

Selected adverse events in this study are defined as adverse events for which additional data collection or analyses will be performed. Selected adverse events do not require immediate reporting if they are not serious or meet the adverse events of special interest definition (see Section 5.2.3).

The following adverse events are considered selected adverse events:

- Thrombocytopenia, including acute thrombocytopenia (events occurring during and within 24 hours following an obinutuzumab infusion)

- Hepatitis B reactivation
- Cardiac events
- TLS
- IRRs
- All infections, including PML
- Neutropenia, including prolonged neutropenia (neutropenia < 1000 cells/ $\mu$ L that does not resolve after 28 days without obinutuzumab treatment) and late-onset neutropenia (neutropenia < 1000 cells/ $\mu$ L occurring  $\geq$  28 days after obinutuzumab treatment has been completed or stopped)
- GI perforation

Events for which additional data collection will be required are PML and hepatitis B reactivation.

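### SAP 6.2.2 times prolonged and late-onset neutropenia only from obinutuzumab, so rituximab-treated DLBCL patients cannot meet either definition

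*SAP*

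**What the plan says.** The selected adverse event table in SAP 6.2.2 has a column for BH39147, and both categories are ticked in it. Each is a neutrophil count below 1.0 × 10⁹/L with a timing rule:

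- Prolonged: an initial low count "that is still present 28 days after treatment with GA101".
- Late-onset: a low count at least "28 days after ga101 infusion has been completed/stopped".

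GA101 is not a general label for anti-CD20 antibodies. Protocol 1.2 states: "Obinutuzumab (also known as GA101) is a novel glycoengineered type II anti-CD20 antibody". The SAP gives no rituximab version of either rule.

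Protocol 5.2.4 has the same restriction. Prolonged neutropenia is neutropenia "that does not resolve after 28 days without obinutuzumab treatment", and late-onset neutropenia occurs at least "28 days after obinutuzumab treatment has been completed or stopped".

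Treatment differs by disease and phase. In the expansion phase, "patients with DLBCL will receive idasanutlin and venetoclax at the RP2Ds in combination with rituximab" (Protocol 3.1.1). The DLBCL bridging cohorts in Protocol 3.1.2.2 are given idasanutlin and venetoclax "in combination with rituximab instead of obinutuzumab". Expansion safety data are summarized by histology (SAP 6, Protocol 6).

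The important rituximab risks listed in Protocol 5.1.2 include "neutropenia (including prolonged neutropenia), TLS, impaired immunization response". Protocol 5.1.2.5 puts delayed-onset neutropenia with rituximab below 1 in 10,000 patients and says the incidence of prolonged neutropenia is not known.

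**The concern.** A category that is ticked for a study but that one of its treatment groups cannot enter gives an uninformative result. A reader who sees no prolonged neutropenia among rituximab-treated patients will take it as an observation, when it follows from the definition.

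This matters because duration is a question the protocol itself raises. Protocol 5.1.5.2, written for venetoclax and idasanutlin with either antibody, anticipates that the combination may lengthen as well as deepen neutropenia. SAP 6.2.2 says that overlapping toxicities anticipated in each protocol must be taken into account, and Protocol Table 14 lists neutropenia among those for rituximab, idasanutlin and venetoclax. The category meant to capture persistence is closed to the patients on that triplet.

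**Working it through.** The documents give no figure for these categories, so there is none to reproduce. The check follows the definitions through the treatment groups and then sizes what an empty cell would fail to show.

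**Who can meet the definitions**

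| Group | Antibody | Can meet the SAP rule? |
|---|---|---|
| FL, all phases | Obinutuzumab | Yes |
| DLBCL, initial escalation (Regimen A) | Obinutuzumab | Yes |
| DLBCL, bridging cohorts | Rituximab | No, no GA101 date exists |
| DLBCL, expansion (about 40) | Rituximab | No, no GA101 date exists |

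The expansion phase has about 80 patients, 40 per disease (Protocol 3.1.3). So 40/80 = 50% of them are outside both definitions, and they make up the whole expansion DLBCL column.

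The protocol's phrase about 28 days without obinutuzumab could be stretched to cover a patient who never had it. The SAP rule cannot, because it needs a GA101 administration from which to count.

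**What an empty cell would hide**

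If a true 0 of 40 were observed, the exact one-sided 95% upper bound on the rate would be 1 − 0.05^(1/40) = 7.2%. Here no such bound may be drawn.

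No rate is documented for the rituximab triplet, so the rates below are assumptions. With an antibody-neutral rule and complete ascertainment, the expected number of events is 40p and the chance of at least one is 1 − (1 − p)^40:

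| Assumed true rate p | Expected events | Chance of at least one |
|---|---|---|
| 1% | 0.4 | 33% |
| 2% | 0.8 | 55% |
| 5% | 2.0 | 87% |
| 10% | 4.0 | 98.5% |

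Under the current SAP rule the qualifying count is zero at every p.

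For late-onset neutropenia the protocol does give a bound for rituximab. At 1 in 10,000, 40 × 0.0001 = 0.004 events are expected, and the chance of any is 1 − 0.9999^40 = 0.4%. That bound is not specific to this triplet, but it makes prolonged neutropenia the main loss.

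**Are the counts collected?**

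Appendix 2 schedules hematology for DLBCL patients as follows:

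- At EOI for patients without consolidation, 6–8 weeks (42–56 days) after Day 1 of the last induction cycle, which is the rituximab day.
- In consolidation, every 2 weeks in the first month and then monthly.
- At EOC, 35 days after the last dose.

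Both the EOI and the EOC sample fall after the 28-day mark. No hematology is scheduled in post-treatment follow-up.

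**Do other outputs fill the gap?**

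Only in part.

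- The broad Neutropenia category and the Grade 3 or higher neutropenia AESI record occurrence, not 28-day persistence. The clause that folds prolonged and late-onset events into the broad category is limited to studies BO29561 to BO29563.
- The adverse event listing (Output 28) shows duration in days, but patient by patient.
- The recovery table (Output 55) counts from the last dose of antibody, so it covers rituximab. It uses windows of months and requires a low count at the last visit before end of treatment or induction, so it cannot show late-onset events.

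**The case against.** The strongest case on the other side has four parts.

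- **The anchor may be deliberate.** Protocol 5.1.1 lists both prolonged and late-onset neutropenia as obinutuzumab risks, and 5.1.1.3 defines both against that drug. Protocol 5.2.4 ties acute thrombocytopenia to an obinutuzumab infusion in the same way. This stands for late-onset neutropenia, which the rituximab risk list does not name. It is weaker for prolonged neutropenia, which that list does name. In either case the SAP does not say that the categories are limited to obinutuzumab.
- **The events are not lost.** This stands. A rituximab patient with prolonged neutropenia still appears in the broad category, in the listings and, at Grade 3 or higher, in the AESI outputs. What is missing is the summary of persistence.
- **Nothing shows what would be printed.** This also stands. A reader might infer that the DLBCL incidence is fixed at 0%. No mock table has a prolonged or late-onset row, Output 42 is laid out by SMQ and preferred term although these are laboratory rules, and the List of Planned Outputs is not among the documents. A zero, a blank, 'not applicable' or no row are all possible.
- **The consequences are easily overdrawn.** A reader might infer that no DLBCL patient can have an event, or that the tables would show the rituximab triplet to be free of neutropenia. The first fails because DLBCL patients in the initial escalation receive obinutuzumab. The second fails because of the outputs just listed. The study is also non-randomized, and no safety comparison between FL and DLBCL is planned.

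**Conclusion.** The point holds in a limited form. Read literally, SAP 6.2.2 excludes every rituximab-treated DLBCL patient from two categories ticked for this study: the bridging cohorts and about 40 expansion patients, half of the expansion phase. Any count shown for them is uninformative. The substantive loss is a summary of prolonged neutropenia on rituximab, idasanutlin and venetoclax; late-onset neutropenia is secondary.

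The conclusion rests on the SAP wording being programmed as written and on GA101 meaning obinutuzumab, which the protocol states. The detection probabilities rest on assumed rates and complete ascertainment, so they illustrate scale and are not forecasts. No efficacy endpoint uses these categories, and the DLT criteria in Protocol 3.1.2.1 treat neutropenia separately. It should be corrected before the safety tables are programmed, as a reporting matter.

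**What to change.** In SAP 6.2.2, count the 28 days in both definitions from the last dose of anti-CD20 antibody, obinutuzumab or rituximab. SAP 6.4.3 already uses an antibody-neutral last dose for neutrophil recovery. Align Protocol 5.2.4 at the next amendment; since Protocol 9.6 requires amendments to go to the IRB/EC and regulatory authorities, an amendment for this alone is not warranted.

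If the obinutuzumab-only scope is intended, say so in SAP 6.2.2 and show 'not applicable' in rituximab-treated columns, so that no zero can be read as a finding.

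The cost is a small wording and programming change. The limit is ascertainment: for DLBCL patients the rule can use only the scheduled samples at EOI, in consolidation and at EOC, plus any unscheduled counts. A footnote should say that no hematology is scheduled in their post-treatment follow-up.

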### **2.1 SAFETY OBJECTIVES**

- To determine the RP2Ds for idasanutlin and venetoclax when given in combination with a fixed dose of obinutuzumab or rituximab during the dose-escalation phase on the basis of the following endpoint:
  - Incidence of DLTs during the first two cycles of study treatment

- To evaluate the safety and tolerability of obinutuzumab or rituximab in combination with idasanutlin and venetoclax during the dose-escalation and expansion phases on the basis of the following endpoints:
  - Nature, frequency, severity, and timing of adverse events, including DLTs
  - Changes in vital signs, ECGs, and clinical laboratory results during and following study treatment administration

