### 3.1.2.3 Use of Modified Continual Reassessment Model for Dose and MTD Determination

The dose escalation will employ a mCRM with overdose control design in order to define the MTD and/or the recommended dose for subsequent cohorts.

The design is based on the primary safety variable, that is, the occurrence of a DLT. The MTD is defined as the dose that maximizes the probability of achieving a DLT rate of 16%–33% (target toxicity interval) and results in a <35% probability of having a DLT rate of >33% (overdose control).

The maximum allowable increments for idasanutlin from the highest dose already tested will not exceed 100 mg, with a minimum increase of 50 mg. The maximum allowable increments for venetoclax from the highest dose already tested will not exceed 200 mg, with a minimum increase of 100 mg.

In addition, the dose of idasanutlin will not be escalated above 600 mg and the dose of venetoclax will not be escalated above 800 mg. The selection of the next dose will be subject to clinical judgment and mandated safety constraints that limit the size of the dose increments. Clinical judgment will always override mCRM recommendations in the dose-selection process.

A detailed algorithm for the selection of the next recommended combination of doses in the dose-escalation procedure is described in [Appendix 6](#). As stated above, only combinations of doses with a <35% probability of having a DLT rate of >33% will be allowed.

Dose escalation will stop when the maximum allowed sample size, 60 patients, has been reached or there is enough confidence in the prediction of the MTD (e.g., at least 6 patients have been recruited at the MTD doses and there is a >40% probability of having a DLT rate of 16%–33%).

The following two marginal models (two-parameter logistic regression), which describe the relationship between DLT and idasanutlin dose in the absence of venetoclax, and conversely, the relationship between DLT and venetoclax dose in the absence of idasanutlin, were considered:

$$\text{logit}\left(p(d_{IDA,i}^*)\right) = \alpha_1 + \beta_1 \log(d_{IDA,i}^*) \quad (1)$$

$$\text{logit}\left(q(d_{VEN,i}^*)\right) = \alpha_2 + \beta_2 \log(d_{VEN,i}^*) \quad (2)$$

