## **6. STATISTICAL CONSIDERATIONS AND ANALYSIS PLAN**

Study data will be summarized separately for dose escalation and expansion phase. Data from the dose-escalation phase will be summarized by dose level and regimen. Data from the expansion phase will be summarized by histologic subtype (i.e., FL or DLBCL).

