#### 2.2.1 Treatment Groups

The treatment arm labels to be included in the outputs are displayed as described below in following order:

Atezolizumab will be replaced by 'Atezo'

Obinutuzumab will be replaced by 'G'

Rituximab will be shown as 'R'

Polatuzumab vedotin will be replaced by 'P'

Venetoclax will be replaced by 'V'

Idasanutlin will be replaced by 'I'

Lenalidomide will be replaced by 'L'

Bendamustine will be replaced by 'B'

CHOP will be shown as 'CHOP'

We also should show dose levels after each treatment. So for illustration purposes, a treatment arm of "Obinutuzumab 1000mg + Polatuzumab vedotin 1mg/kg + Lenalidomide 10mg" would be shown as "G (1000MG) P (1MG/KG) L (10MG)", or "Obinutuzumab 1000mg + Atezolizumab 1mg + CHOP" would be shown as "Atezo (1MG) - G (1000MG) - CHOP".

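### For BH39147 the SAP shows no DLT analysis, groups escalation data without venetoclax schedule or regimen, and defines two adverse events of special interest in ways that need realigning

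*SAP*

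**What the plan says.** **DLT.** Protocol 2.1 bases the RP2D objective on this endpoint: "Incidence of DLTs during the first two cycles of study treatment". Protocol 3.1.2.3 adds: "The design is based on the primary safety variable, that is, the occurrence of a DLT". In the SAP, DLT appears once, as the row "Dose Limiting Toxicity" of the selected-AE table in 6.2.2, defined by a CRF tickbox. SAP section 1 does not list BH39147 among the studies covered, although the tables in 6.2.2 have a BH39147 column.

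**Grouping.** Protocol section 6: "Data from the dose-escalation phase will be summarized by dose level and regimen". SAP section 6: "Data from the dose-escalation/safety run-in phase will be summarized by cohort (assigned dose level". For arm labels, SAP 2.2.1 uses a letter per drug and then says: "We also should show dose levels after each treatment".

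**Events of special interest.** Protocol 5.2.3 lists Grade ≥3 neutropenia (with febrile neutropenia) and second malignancies, the latter with no onset rule. SAP 6.2.2 retrieves the first with "SMQ HAEMATOPOIETIC LEUKOPENIA (narrow" and limits the second to events "starting 6 months after the first study drug intake or later".

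**The concern.** A dose-finding study should report its primary safety variable against the right denominator, for each regimen actually given. As written, the SAP shows no place where that is done for BH39147. Its grouping rule could also put patients with different venetoclax exposure, or with a different start of the combination, into one column. A reader of the clinical study report could then not reconstruct from the tables why a dose, a 5- or 10-day venetoclax schedule, or Regimen A or B was chosen. The two event definitions matter less, but they make the reported categories differ from the protocol's own list or from another row of the same SAP.

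**Working it through.** No sample-size or error-rate calculation applies. The check sets the texts side by side.

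**1. Is the blank DLT cell real?** The study columns run BO29563, BO29562, BO29561, BH29812, BH39147, GO29833, GO29834. Reading each row by column position gives:

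| Row in SAP 6.2.2 | Ticked for |
|---|---|
| Dose-limiting toxicity | BH29812 |
| Prolonged neutropenia | BH29812, BH39147 |
| Drug-drug interactions | BO29562 |
| Secondary malignancy | all seven |

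The other rows fall where one would expect, so a column shift does not explain the blank.

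**2. Is DLT covered elsewhere?** SAP section 10 says that it contains all output templates. Outputs 1 to 77 include no DLT table or listing. Output 3 has three populations: enrolled, safety evaluable and efficacy evaluable. A tick alone would not be enough, because it brings DLT into the selected-AE outputs, which use the safety population. Protocol 3.1.2 treats as non-evaluable, and replaces, patients who leave the two-cycle window early or miss more than one dose for reasons other than a DLT. Those who received any dose stay in the safety population and would be counted in the denominator.

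**3. What does the label rule do?** Apply SAP 2.2.1 to Protocol Table 1:

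| Cohort | Obinutuzumab | Idasanutlin | Venetoclax | Label |
|---|---|---|---|---|
| Safety cohort | 1000 mg | 100 mg | 200 mg, Days 1–5 | G (1000MG) V (200MG) I (100MG) |
| Cohort 1 | 1000 mg | 100 mg | 200 mg, Days 1–10 | G (1000MG) V (200MG) I (100MG) |

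Venetoclax per cycle is 5 × 200 = 1000 mg against 10 × 200 = 2000 mg, a two-fold difference under one label. The FL bridging cohort (Protocol 3.1.2.2) repeats the last dose tested, now in Regimen B, so it takes the label of the Regimen A cohort at that dose. In Regimen B, Cycle 1 is obinutuzumab alone. The triplet is therefore given in one of the two DLT-window cycles, against both in Regimen A. The DLBCL bridging cohorts stay separate because rituximab has its own letter.

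**4. Do the two event definitions match?**
- *Neutropenia.* The selected-AE row for BH39147 uses the sponsor's neutropenia grouping and keeps the leukopenia query for GO29833 and GO29834. The special-interest row uses the leukopenia query for BH39147. One study thus has two retrievals for one event.
- *Second malignancies.* The protocol sets no lag. The SAP sets six months from first study drug, so an earlier case does not enter the category.

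**The case against.** The SAP is to be read with the List of Planned Outputs, which is not available here and may contain a DLT table. This stands as a limit: the finding is that no DLT output is visible, not that none will be made. The protocol's own selected-AE list (5.2.4) does not name DLT, so the blank cell agrees with that list. That is true, but it leaves the primary safety endpoint with no analysis in either place. The protocol already defines who is DLT-evaluable. That also stands, and the SAP needs only to adopt that rule.

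On grouping, the word cohort, taken alone, would keep the protocol's named cohorts apart, and the label examples are offered as illustrations. But the SAP explains cohort as assigned dose level, and a label built from drug and dose cannot show schedule or regimen. The ambiguity is real, and a wording change resolves it.

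On neutropenia, a reader might infer that the leukopenia query inflates the rate. The documents do not show this, because they do not give the query's term list and its breadth can be judged only from its name. What stands is the inconsistency within the SAP.

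On second malignancies, a reader might infer that early cases are lost, or that rituximab patients who stop early cannot contribute. Neither follows. Early cases still appear in the all-AE listing and table (Outputs 28 and 37). After the 90-day period, serious events believed related to treatment remain reportable (Protocol 5.6), and SAP 6.2.1 sets no upper time limit on follow-up tables.

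**Conclusion.** The point holds as a mismatch between SAP and protocol in four places. The missing DLT analysis is the main one, the grouping and label wording comes second, and the two event definitions are minor.

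A reader might infer that the RP2D, the venetoclax schedule or the regimen is chosen on these summaries. The documents do not support that. Protocol 3.1.2.2 has the Sponsor, in consultation with investigators, decide after each cohort from the mCRM recommendation and the accumulating data. Protocol 3.1.4 gives the IMC the data needed for the RP2Ds. Protocol 3.1.2.3 plans independent models per venetoclax schedule, with a joint model as an option. The effect is therefore on the safety reporting in the clinical study report and on how it supports the RP2D.

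The only size that the documents give is the two-fold difference in venetoclax per cycle between the safety cohort and Cohort 1. No DLT counts are available and no planned DLT table is visible, so a distortion of the DLT rate cannot be quantified. The conclusion assumes that the List of Planned Outputs does not already supply the table and that the SAP's grouping and label text is applied literally.

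**What to change.** 1. Tick DLT for BH39147 in SAP 6.2.2 and name the study in SAP section 1. Add a DLT-evaluable population to Output 3, using the non-evaluability rules in Protocol 3.1.2. Add one table of patients with a DLT over evaluable patients, by antibody, idasanutlin dose, venetoclax dose, venetoclax schedule and regimen.
2. Align SAP section 6 and 2.2.1 with Protocol section 6 by adding venetoclax schedule and regimen to the grouping and to the label.
3. For the Grade ≥3 neutropenia event of special interest, use the neutropenia grouping that the SAP already applies to BH39147, restricted to Grade ≥3.
4. Report second malignancies from first dose, with onset at six months or later as a sub-row.

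The cost is SAP edits and programming for one population and one output. DLTs already reach the Sponsor through the Adverse Event eCRF (Protocol 5.4.2.2), so no new data are needed. The study team should confirm that the BH39147 form carries the tickbox on which the SAP's DLT row relies.
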